7.3 FU duration

Data file:	Notes	Variable	Variable	Variable	Nominal
Identifier		name	label	level	values
patient_					
display_id_full					
· · · · -	descriptive and	FU_duration_SAR	Days from enrollment to termination	scale	n.a
	cumulative				

8 Analyses: Baseline

8.1 Analysis set

All analyses are performed for the enrollment analysis set1.

8.2 Variables

Baseline / demographics

Data file, identifier patient_ display_id_full	Notes	Variable name	Variable label		Nominal values
baseline_general	descriptive	dmage	Age [Years]	scale	n.a.
		dmsex	Gender	nominal	∘ Female ∘ Male
		dmrace	Ethnicity	nominal	 Caucasian Black Asian Indigenous Other
	case listing for dmrace = Indigenous	corace	Specification of indigenous ethnicity	text	n.a.
	case listing for dmrace = Other	coraceot	Specification of other ethnicity	text	n.a.

Baseline / physical examination

Data file,	Notes	Variable	Variable	Variable	Nominal
identifier		name	label	level	values
patient_					
display_id_full					
baseline_general	descriptive	vshght	Height [cm]	scale	n.a.
		vswght	Weight [kg]	scale	n.a.
		vsbmi	BMI [kg/m2]	scale	n.a.

¹ analysis_set_enr_SAR = Yes

Baseline / therapy indication

Data file, identifier patient_ display_id_full	Notes	Variable name	Variable label	Variable Ievel	Nominal values
baseline_general	descriptive	cecrt	CRT indication given	nominal	∘Yes ∘ No
	descriptive for cecrt = Yes	cecrttyp	Type of CRT indication	nominal	 CRT indication in sinus rhythm CRT indication in atrial fibrillation CRT indication and conventional pacing indication Other
	case listing for cecrttyp = Other	cocrtoth	Specification of other CRT indication	text	n.a.
	descriptive	cebcind	Main indication for bradycardia therapy	nominal	o Sinus node disease o AV block o AF with bradycardic response o Reflex syncope o Bundle branch block o Other
	case listing for cebcind <> Other	cobcind	Details on indication for bradycardia therapy	text	n.a.
	case listing for cebcind = Other	cobcoth	Specification of other main bradycardia indication	text	n.a.
	descriptive	prim	Previous device implanted	nominal	∘Yes ∘ No
	descriptive for prim = Yes	primdvty	Type of previously implanted device	nominal	o Pacemaker o ICD o CRT pacemaker o CRT ICD o Implantable loop recorder

Medical history / known cardiac history - heart failure

Data file, identifier patient_display_id_full	Notes	Variable name	Variable label	Variable level	Nominal values
medical_	descriptive	mhhf	History of heart failure	nominal	∘Yes ∘ No
history	descriptive for mhhf = Yes	cvnyha	Current NYHA classification	nominal	○ I - Code = 1○ II - Code = 2○ III - Code = 3○ IV - Code = 4
		mhhfe	Primary HF etiology	nominal	 Ischemic Non-ischemic
		mhhftyp	Type of HF	nominal	Left heart failureRight heart failureGlobal heart failure
		hohf	Hospitalization for worsening of heart	nominal	∘ Yes ∘ No

Medical history / known cardiac history - coronary artery disease

Data file, identifier	Notes			Variable level	Nominal values
patient_ display_ id_full					
	descriptive	mhcad	History of coronary artery disease	nominal	∘ Yes ∘ No
history	descriptive for mhcad = Yes	mhaccs	Prior acute coronary syndrome (any type)	nominal	∘ Yes ∘ No
	descriptive for mhaccs = Yes	mhmi	Prior myocardial infarction	nominal	∘ Yes ∘ No
	descriptive for mhcad = Yes	prrvc	Prior revascularization (PCI or CABG)	nominal	∘ Yes ∘ No

Medical history / known cardiac history - brady- and tachyarrhythmias

Data file, identifier patient_display_	Notes	Variable	Variable label	Variable level	Nominal values
id_full medical_	descriptive	mhsss	History of sick sinus syndrome	nominal	∘ Yes ∘ No
history	descriptive	mhavb	History of AV block	nominal	∘ Yes ∘ No
,	descriptive for mhavb = Yes		Type of AV block	nominal	o AV block I° o AV block II° o AV block III°
	descriptive	mhbbb	History of bundle branch block	nominal	o Yes ∘ No
	descriptive for mhbbb = Yes	, ,	Type of bundle branch block	nominal	○ LBBB○ RBBB○ Other
	case listing for mhbbbtyp = Other	cobbbtyp	Specification of other type of bundle branch block	text	n.a.
	descriptive	mhcnddot	History of other type of conduction disease	nominal	∘ Yes ∘ No
	case listing for mhcnddot = Yes	cocnddot	Specification of other type of conduction disease	text	n.a.
	descriptive	mhafb	History of atrial fibrillation	nominal	∘ Yes ∘ No
	descriptive for mhafb = Yes	cvafbtyp	Type of atrial fibrillation	nominal	ParoxysmalPersistentLong-standing persistentPermanent
	descriptive	mhava	History of other atrial/supraventricular arrhythmias	nominal	∘ Yes ∘ No
	descriptive for	mhafl	History of atrial flutter	nominal	o Yes ∘ No
	mhava = Yes	mhat	History of atrial tachycardia	nominal	∘ Yes ∘ No
		mhsvt	History of supraventricular tachycardia	nominal	∘ Yes ∘ No
		mhavaoth	History of other type of atrial/supraventricular arrhythmias	nominal	∘ Yes ∘ No
	case listing for mhavaoth = Yes	coavaoth	Specification of other type of atrial/supraventricular arrhythmias	text	n.a.
	descriptive	mhva	History of ventricular arrhythmia	nominal	∘ Yes ∘ No
	case listing for mhva = Yes	cova	Specification of history of ventricular arrhythmia	text	n.a.
	descriptive	mhci	Known chronotropic incompetence	nominal	∘ Yes ∘ No

Medical history / known comorbidities

Data file, identifier patient_display_id full	Notes	Variable name	Variable label	Variable level	Nominal values
medical_	descriptive	mhhp	Hypertension (including well-controlled)	nominal	∘ Yes ∘ No
history	·	mhphp	Pulmonary hypertension	nominal	∘ Yes ∘ No
,		mhvhd	Valvular heart disease	nominal	∘ Yes ∘ No
	descriptive for	mhaova	Aortic valve affected	nominal	∘ Yes ∘ No
	mhvhd = Yes	mhmiva	Mitral valve affected	nominal	∘ Yes ∘ No
	descriptive for	mhmiin	Mitral insufficiency	nominal	∘ Yes ∘ No
	mhvhd = Yes and cecrt = Yes	mhmist	Mitral stenosis	nominal	∘ Yes ∘ No
	descriptive for	mhtrva	Tricuspid valve affected	nominal	∘ Yes ∘ No
	mhvhd = Yes	mhpuva	Pulmonary valve affected	nominal	∘ Yes ∘ No
	case listing for	covhd	Further specification of valvular heart	text	n.a.
	mhvhd = Yes		disease (e.g. type, severity)		
	descriptive	mhcvd	History of cerebrovascular disease (e.g. TIA/Stroke)	nominal	∘ Yes ∘ No
		mhpvad	Peripheral vascular/arterial disease	nominal	∘ Yes ∘ No
		mhasth	Asthma or other chronic lung disease (except COPD)	nominal	∘ Yes ∘ No
		mhcopd	Chronic obstructive pulmonary disease (COPD)	nominal	∘ Yes ∘ No
		mhckd	Chronic renal insufficiency / chronic kidney disease (CKD) (i.e. eGFR < 60)	nominal	∘ Yes ∘ No
		mhsap	Sleep apnea	nominal	∘ Yes ∘ No
	descriptive for	mhsaptyp	Type of sleep apnea	nominal	 Central
	mhsap = Yes				 Obstructive
					Mixed
	descriptive	mhlivr	Chronic liver disease	nominal	∘ Yes ∘ No
		mhdiam	Diabetes mellitus	nominal	∘ Yes ∘ No
		mhanem	Anemia	nominal	∘ Yes ∘ No
		mhcncr	Cancer	nominal	∘ Yes ∘ No
		mhhplp	Hyperlipidemia	nominal	∘ Yes ∘ No
		mhdprssn	Depression	nominal	∘ Yes ∘ No
		mhcmboth	Other comorbidities	nominal	∘ Yes ∘ No
	case listings mhcmboth =Yes	cocmboth	Specification of other comorbidities	text	n.a.

Cardiac diagnosis / ECG

Data file, identifier patient_ display_ id_full	Notes	Variable name		Variable level	Nominal values
cardiac_ diagnostics	descriptive	preg	ECG recording done within 3 months prior to enrollment		∘ Yes ∘ No
	descriptive for preg	eghrt	Heart rate [bpm]	scale	n.a.
	= Yes	cvegarh	Atrial rhythm during ECG recording	nominal	 Sinus rhythm Atrial fibrillation Atrial flutter/other SVT Atrial paced rhythm Other
	case listing for cvegarh = Other		rhythm during ECG recording	text	n.a.
	descriptive for preg = Yes	cvegvrh	Ventricular rhythm during ECG	nominal	o Intrinsic - atrial conducted o Intrinsic - escape rhythm o Ventricular paced rhythm o Other
	case listing for cvegvrh = Other	coegvrh	Specification of other ventricular rhythm during ECG recording	text	n.a.
	descriptive if not blank	egpri	PR interval [ms]	scale	n.a.
	descriptive for	egqrs	, , , , ,	scale	n.a.
	cvegvrh = Intrinsic - atrial conducted OR Intrinsic - escape rhythm	egqrsm	QRS morpholgy	nominal	NormalLBBBRBBBIndeterminate

Cardiac diagnosis / left ventricular ejection fraction (LVEF)

Data file, identifier		Variable name		Variable level	Nominal values
patient_ display_ id_full					
cardiac_	descriptive	ehlvefas	LVEF assessed within 3 months prior to enrollment	nominal	∘ Yes ∘ No
diagnostics	Descriptive for	ehlvef	Left ventricular ejection fraction [%]	scale	n.a.
	ehlvefas = Yes				

Medication

Medication is recorded on a continuous medication log documenting free text for trade names. An allocation between trade names and medication categories will be continuously maintained and updated at least during the blind review prior to any data analysis.

identifier patient_	Notes			Variable level	Nominal values
display_ id_full					
medication_ log_details	no report	cmbl	Baseline medication	nominal	∘ Yes ∘ No
	no report	cmtrt	Trade name	text	n.a.

Data file, identifier patient_display_id_full			Variable label	Variable level	Nominal values
data_SAR	descriptive	aceinhib	BL med: ACE inhibitors	nominal	∘ Yes ∘ No
	for cmbl =	aldost_block	BL med: Aldosterone blocker	nominal	∘ Yes ∘ No
	Yes	angiotens_rec_block	BL med: Angiotensin receptor blocker	nominal	∘ Yes ∘ No
		antiarrhythmics	BL med: Antiarrhythmics	nominal	∘ Yes ∘ No
		anticoagulation	BL med: Anticoagulation	nominal	∘ Yes ∘ No
		antiplatelets	BL med: Antiplatelets	nominal	∘ Yes ∘ No
			BL med: Betablocker (excluding sotalol)	nominal	∘ Yes ∘ No
		ccblocker	BL med: Calcium channel blocker	nominal	∘ Yes ∘ No
		digitalis	BL med: Digitalis	nominal	∘ Yes ∘ No
		diuretics	BL med: Diuretics (other than	nominal	∘ Yes ∘ No
			Aldosterone blocker)		
		statins	BL med: Statins	nominal	∘ Yes ∘ No
		other_cv_med	BL med: Other cardiovascular medication	nominal	∘ Yes ∘ No
		non_cv_med	BL med: Non-cardiovascular medication	nominal	∘ Yes ∘ No

8.3 Missing, unused or spurious data

See chapter 5.

8.4 Hypotheses & statistical tests

There are no pre-defined statistical hypotheses.

9 Analyses: Primary endpoint(s)

CIP chapter 8.1.3.1 Primary endpoints

As no hypothesis has been defined, no primary endpoint is defined either.

10 Analyses: Secondary endpoint

CIP chapter 8.1.3.2 Secondary endpoints

Due to the low number of use cases per feature, no secondary endpoints are defined.

11.1 Baseline characteristics and medical history

See chapter 8.

11.2IPG-related SADE-free rate (see definition below)

CIP chapter 8 Design of the CliInical Investigation 8.1. General considerations

...

Definition of SADEs to be taken into account for the calculation of the SADE-free rate: SADEs will be adjudicated internally, whereby the seriousness and device relatedness will be reexamined.

If any amply documented external physical influence (e.g. accident, sport, twiddling) or other causative AE led to the SADE, the SADE does not contribute to the calculation of the SADE-free rate. Only SADEs directly related to the investigational device (SADE-d) will be included in the analysis. SADEs which are securely related to the implantation procedure (SADEp) (e.g. pocket infection, etc.) will not be considered for the analysis. Furthermore Twiddler's syndrome will not be considered for the analysis either.

...

CIP chapter 12 Statistical Design and Analysis 12.2. Descriptive statistics

. . .

The SADE-free rate is calculated using the Kaplan-Meier estimate after 12 months.

Data file, identifier record_id				Variable level	Nominal values
internal_ adjudication	no report	aestdt	Onset date	date	n.a.
adjudication			Adverse Event is relevant for SADE-free rate	nominal	∘ Yes ∘ No

Data file, identifier patient_ display_ id_full	Notes	Variable name		Variable level	Nominal values
data_SAR	no report	date_implantation_SAR	Date of implantation	date	n.a.
		date_terminaton_SAR	Date of study termination	date	n.a.
		date_1stsade_SAR	Date of first SADE	date	n.a.
		date_censoring_SAR	Date of censoring (date_1stsade_SAR OR date_terminaton_SAR)	date	n.a.
	descriptive and 95% CI,	any_sade_SAR	Any Serious Adverse Device Effect based on internal adjudication	nominal	YesNo
	Kaplan Meier analysis	days_impl_censoring_SAR	Days from implantation to censoring	date	n.a.

Data file, identifier patient_ display_ id_full	Notes	Variable name	Variable label	Variable Level	Nominal values
internal_	case listing	aestdt	Onset date	date	n.a.
adjudication		primdt	Date of implantation	date	n.a.
		aerelidv	Adverse Event is related to the investigational device (device related ADE)	nominal	○ Not related○ Unlikely○ Possible○ Probable○ Causal relationship
		corelidv	Please specify	text	n.a.
		aeser	Adverse Event is serious	nominal	∘ Yes ∘ No
		aerelset	Adverse Event is relevant for SADE-free rate	nominal	∘ Yes ∘ No
		corelset	Please specify reason for "No"		∘Yes ∘No

Data file, identifier patient_display_id_full	Notes	Variable name	Variable label	Variable Level	Nomin al values
data_SAR	descriptive	any_ade_SAR	Any Adverse Device Effect (serious or non-serious) based on internal adjudication	nominal	∘Yes ∘No
		any_sade_SAR	Any Serious Adverse Device Effect based on internal adjudication	nominal	∘Yes ∘No
		any_dd_SAR	Any Device Deficiency	nominal	∘ Yes ∘ No
		n_ade_SAR	Number of Adverse Device Effects (serious or non-serious) based on internal adjudication	metric to be reported as nominal	○1 ○2 •••
		n_sade_SAR	Number of any Serious Adverse Device Effects based on internal adjudication	metric to be reported as nominal	∘1 ∘2
		n_dd_SAR	Number of any Device Deficiencies	metric to be reported as nominal	○1 ○2

Lead Measurements

11.3Lead measurements (sensing amplitude, pacing threshold, pacing impedance at implantation and at each follow-up and/or via Home **Monitoring**)

Data file, identifier Patient_display _id_full	Notes		Variable label	Variable Ievel	Nominal values
lead_ measurements	descriptive	prvisit	Visit	nominal	o Implantation o Pre-hospital discharge o 1-Month Follow-up o 3-Month Follow-up o 12-Month Follow-up
	descriptive by prvisit	durvmna	measurements available No RV lead measurements available		oRA lead measurements not done oRA lead not implanted/not active oRA lead measurements not done oRA lead not implanted/not active
			No LV lead measurements available	nominal	oRA lead measurements not done oRA lead not implanted/not active

Lead Measurements - Atrium (RA)

Data file, identifier patient_ display_ id_full	Notes	Variable name	Variable label	Variable level	Nominal values
lead_ measurements		durasa	RA sensing amplitude [mV], mean value	scale	n.a
		cvrasrh	RA rhythm during sensing measurements	nominal	Sinus rhythmAtrial fibrillationAtrial flutter/other SVTOther.
	case listing for cvrasrh = Other		Specification of other RA rhythm during sensing measurements	text	n.a.
		durapt	RA pacing threshold [V]	scale	n.a.
	by prvisit		Pulse width for RA pacing threshold measurement [ms]	scale	n.a.
		durapi	RA pacing impedance [Ohm]	scale	n.a.

Lead Measurements - Right Ventricle (RV)

Data file, identifier patient_ display_ id_full	Notes	Variable name	Variable label	Variable level	Nominal values
lead_ measurements		durvsa	RV sensing amplitude [mV], mean value	scale	n.a
		cvrvsrh	Ventricular rhythm during sensing measurements	nominal	o Intrinsic - atrial conducted o Escape rhythm o Other
	case listing for cvrvsrh = Other	corvsrho	Specification of other ventricular rhythm during sensing measurements	text	n.a
		durvpt	RV pacing threshold [V]	scale	n.a
	by prvisit	durvptpw	Pulse width for RV pacing threshold measurement [ms]	scale	n.a
		durvpi	RV pacing impedance [Ohm]	scale	n.a

Coronary Sinus (CS) Lead Measurements - Left ventricle (LV)

			rents - Left Ventricle (LV)		
identifier	Notes	Variable name	Variable label	Variable level	Nominal values
patient_					
display_					
id_full					
_		dulvsv	Permanently programmed	nominal	oLV1 tip to LV2 ring (bipolar)
measurements	by prvisit		LV sensing vector		oLV1 tip to Can (unipolar)
		dulvsa	LV sensing amplitude [mV], mean value	scale	n.a
		dulvpv	Permanently programmed	nominal	oLV1 tip to Can
			LV pacing vector		oLV1 tip to LV2 ring
					oLV1 tip to LV3 ring
					oLV1 tip to LV4 ring
					oLV1 tip to RV2 ring
					oLV2 ring to Can
					oLV2 ring to LV1 tip
					oLV2 ring to LV3 ring
					oLV2 ring to LV4 ring
					oLV2 ring to RV2 ring
					oLV3 ring to Can
					oLV3 ring to LV1 tip
					oLV3 ring to LV2 ring
					oLV3 ring to LV4 ring
					oLV3 ring to RV2 ring
					oLV4 ring to Can
					oLV4 ring to LV1 tip
					oLV4 ring to LV2 ring
					oLV4 ring to LV3 ring
					oLV4 ring to RV2 ring
		dulvpt	LV pacing threshold [V]	scale	n.a
		dulvptpw	Pulse width for LV pacing threshold measurement [ms]	scale	n.a
		dulvpi	LV pacing impedance [Ohm]	scale	n.a

11.4 Evaluation of appropriate sensing and pacing performance for all available channels (RA, RV, LV) at implantation and at each follow-up

System Performance

Data file, identifier patient_ display_ id_full	Notes	Variable name	Variable label	Variable level	values
lead_	descriptive by	durasad	Adequate RA sensing	nominal	∘Yes ∘ No
measurements	prvisit	durasrea	Reason for inadequate RA sensing	nominal	OversensingUndersensingOther
	case listing for durasrea = Other	corasrea	Please specify reason for inadequate RA sensing	text	n.a
	descriptive by	durapad	Adequate RA pacing	nominal	∘Yes ∘ No
	prvisit	duraprea	Reason for inadequate RA pacing	nominal	○ Exit block: no capture at maximum output○ Other
	case listing for duraprea = Other	coraprea	Please specify reason for inadequate RA pacing	text	n.a.
	descriptive by	durvsad	Adequate RV sensing	nominal	∘Yes ∘ No
	prvisit	durvsrea	Reason for inadequate RV sensing	nominal	○ Oversensing○ Undersensing○ Other
	case listing for durvsrea = Other	corvsrea	Please specify reason for inadequate RV sensing	text	n.a
	descriptive by prvisit	durvpad	Adequate RV pacing	nominal	∘Yes ∘ No
		durvprea	Reason for inadequate RV pacing	nominal	○ Exit block: no capture at maximum output○ Other
	case listing for durvprea = Other	corvprea	Please specify reason for inadequate RV pacing	text	n.a.
	descriptive by	dulvsad	Adequate LV sensing	nominal	∘Yes ∘ No
	prvisit	dulvsrea	Reason for inadequate LV sensing	nominal	OversensingUndersensingOther
	case listing for dulvsrea = Other	colvsrea	Please specify reason for inadequate LV sensing	text	n.a
	descriptive by	dulvpad	Adequate LV pacing	nominal	∘Yes ∘ No
	prvisit	dulvprea	Reason for inadequate LV pacing	nominal	○ Exit block: no capture at maximum output○ Other
	case listing for dulvprea = Other	colvprea	Please specify reason for inadequate LV pacing	text	n.a.

11.5Implantation and device details

Implantation

Data file,	Notes	Variable	Variable	Variable	Nominal
identifier		name	label	level	values
patient_					
display_					
id_full					
implantation	descriptive	primtyp	Type of implantation	nominal	o De-novo system
					∘ Upgrade system
					o Device exchange
		prxrt	Total X-ray time [min]	scale	n.a.
		prprtm	Total procedure time [min]	scale	n.a.
			Please specify untypical circumstances	text	n.a.
	qsutcrc = Yes		influenced the implantation time		

Device details

Jevice detai		ı			
Data file, identifier patient_ display_ id_full	Notes	Variable name	Variable label	Variable level	Nominal values
device_log_ details	descriptive with "Unknown"	dxdvloc	Implantation site	nominal	o Left o Right
	to be analyzed as missing data	dxdvpos	Implant position	nominal	o Sub-cutaneous o Sub-pectoral
	descriptive for Pacemaker OR CRT-P	didvtyp	General type of device	nominal	o Pacemaker SR-T o Pacemaker DR-T o CRT-P
	descriptive for RA Lead, RV Lead and LV Lead with "Unknown" to be analyzed as missing data	dxdvmtd	Implantation approach	nominal	 Subclavian access Cephalic access Extrathoracic subclavian access Axillary access Other Unknown
	case listing for dxdvmtd = Other	codvmtd	Specification of other implantation approach	text	n.a.
	descriptive for didvtyp = RA lead	diramdl	RA lead model	nominal	see Lead Models in CDDS
		dxraloc	RA lead placement	nominal	Right atrial appendageLateral wallSeptal wallOther
	descriptive for didvtyp = RV lead and with "Unknown" to be analyzed as missing data	dirvmdl	RV lead model	nominal	see Lead Models in CDDS
		dxrvloc	RV lead placement	nominal	o Apical o Septal o Outflow tract o Other o Unknown
	descriptive for	dilvmdl	LV lead model	nominal	see Lead Models in CDDS
	didvtyp = LV lead and with "Unknown" to be analyzed as missing data	dxIvIoc	LV lead placement	nominal	o Posterolateral vein o Middle cardiac vein o Lateral vein o Anterolateral vein o Anterior vein o Posterior vein o Other

dxlvtloc

dulvtyp

nominal

Wall location of LV lead tip nominal

Type of LV lead

o Unknown

○ Basal segment○ Mid segment○ Apical segment○ Unknown

○ Coronary sinus lead○ Endocardial lead○ Epicardial lead

			Specification of lead model	nominal	n.a.
case lis lead pla Other	ting for concerned to		Specification other lead placement	text	n.a.
descript			Status of device	nominal	o Implanted and active o Deactivated but still connected and implanted o Capped but still implanted o Explanted and returned to manufacturer o Explanted and discarded o Attempted implantation, then returned to manufacturer o Attempted implantation, then discarded o Other
case lis dtdvsta Implant active	t <> pred and dt	tdvstat rimstdt texdt idvtyp		n.a.	n.a.
case lis dtdvsta	ting for co		Specification of other status of device	text	n.a.

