2.4 General information

This SAP may contain verbatim excerpts from the version of the CIP specified at the cover sheet. Such excerpts are *italicized with light blue background*.

The main aspects and the design of the clinical investigation are presented in chapters 2-3.

General statistical procedures are summarized in chapter 5. Those methods are used in case there is no other specification within this document.

Analysis set(s) and other global variables are defined in detail in chapter 6.

Descriptive and inferential statistical analyses for endpoint(s) are handled in following chapters. Thereby the following statistical considerations are specified:

- Analysis set: Definition of the analysis population (e.g. Intention-to-Treat or Per-Protocol for controlled clinical investigations or all patients with valid informed consent for singlearm clinical investigations)
- Variable characteristics: Description of all relevant variables (directly addressable from validated tools, e.g. CDMS or CDW, and derived variables) such as variable name, variable label, variable values, and data type.
- Derived variables, if applicable: For variables, which are not directly addressable from validated tools but are derived from other variables, pseudo-code or other instructions for the variable construction shall be provided.
- Missing, unused or spurious data: Specification of all data to be excluded from the specific analysis, e.g. data measured after a pre-specified point in time or implantation date after pre-hospital discharge date; specification whether and –if applicable– how to impute missing data.
- Data analysis: Description of descriptive, exploratory, and confirmatory analyses in text, tables, or pseudo-code shall be provided for unambiguous data analysis.

All variables are defined in tables using the following columns:

Data file: Name of a data file exported from the CDMS and CDW and unique identifier, if applicable (e.g. patient-specific "patient_display_ID_full" or event-specific record_ID); new data files ("data_SAR") may be generated by merging all relevant data from the original CDMS data files and generating derived variables;

Notes: Information whether data shall be presented with "descriptive" methods as defined in this SAP, data for "case listings" of original data for each patient specified, or "no report" for data needed for generating derived variables only;

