11.2 IPG-related SADE-free rate (see definition below)

SAP 2-0:

Data file, identifier patient_ display_ id_full	Notes	Variable name	Variable label	Variable Level	Nominal values
internal_	case listing	aestdt	Onset date	date	n.a.
adjudication		primdt	Date of implantation	date	n.a.
		aerelidv	Adverse Event is related to the investigational device (device related ADE)	nominal	 ○ Not related ○ Unlikely ○ Possible ○ Probable ○ Causal relationship
		corelidv	Please specify	text	n.a.
		aeser	Adverse Event is serious	nominal	∘Yes ∘No
		aerelset	Adverse Event is relevant for SADE-free	nominal	∘ Yes
			rate		o No
		corelset	Please specify reason for "No"		∘ Yes
]				o No

Corrections:

If no SADEs occurred during the observation period, the binomial confidence interval is calculated in addition to the Kaplan-Meier estimator. Taking into account all patients of the analysis set and in addition only a subgroup of patients with documented 12-month follow-up.

Data file, identifier patient_ display_ id_full	Notes		Variable label	Variable Level	Nominal values
	case listing if relevant	aestdt	Onset date	date	n.a.
adjudication	for SADE-free rate	primdt	Date of implantation	date	n.a.
	descriptive if evaluated	aeser	Adverse Event is serious	nominal	∘ Yes
					⊙ No
		aerelidv	Adverse Event is related to	nominal	○ Not related
			the investigational device		o Unlikely
			(device related ADE)		o Possible
					o Probable
					○ Causal relationship
		aerelset	Adverse Event is relevant for	nominal	∘Yes
			SADE-free rate		∘ No
	descriptive for aerelset	corelidv	Please specify	text	o n.a.
	= No	corelset	Please specify reason for "No"	text	o n.a.

11.3 Lead measurements (sensing amplitude, pacing threshold, pacing impedance at implantation and at each follow-up and/or via Home Monitoring)

Coronary Sinus (CS) Lead Measurements - Left ventricle (LV)

SAP 2-0:

Data file,	Notes	Variable	Variable	Variable	Nominal
identifier		name	label	level	values
patient_					
display_					
id_full					
lead_	descriptive	dulvsv	Permanently programmed	nominal	oLV1 tip to LV2 ring (bipolar)
measurements	by prvisit		LV sensing vector		oLV1 tip to Can (unipolar)

Correction:

Data file, identifier patient_ display_ id_full	Notes		Nominal values
measurements		Permanently programmed LV sensing vector	oLV1 tip to LV2 ring (bipolar) oLV1 tip to Can (unipolar)

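### Does using one flag, any_sade_SAR, for both the SADE-free rate and the general any-SADE row leave the rate undefined?

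*SAP*

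**What the plan says.** SAP 11.2 quotes the CIP definition of the events behind the SADE-free rate. The restriction is explicit: "Only SADEs directly related to the investigational device (SADE-d) will be included in the analysis". If an external influence or another adverse event caused the SADE, "the SADE does not contribute to the calculation of the SADE-free rate". Events securely tied to the implantation procedure, and Twiddler's syndrome, are also left out.

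The first table after the definition takes two event-level fields from the internal adjudication file: the onset date and the item recording whether the event is relevant for the rate (`aerelset`). Both carry the note *no report*, which SAP 2.4 reserves "for data needed for generating derived variables only".

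The next table holds `date_1stsade_SAR`, the censoring date and `any_sade_SAR`, labelled "Any Serious Adverse Device Effect based on internal adjudication". This flag is marked for a 95% interval and the Kaplan-Meier analysis.

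A later table in 11.2 repeats `any_sade_SAR` with the same label. There it stands beside `any_ade_SAR` ("Any Adverse Device Effect (serious or non-serious) based on internal adjudication"), `n_sade_SAR` ("Number of any Serious Adverse Device Effects based on internal adjudication") and the device deficiency rows.

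The Erratum adds to 11.2: "If no SADEs occurred during the observation period, the binomial confidence interval is calculated in addition to the Kaplan-Meier estimator". It limits the dated listing ("case listing if relevant" for the rate), and reports seriousness, device relation, relevance and the reasons for a negative relevance decision descriptively. It does not rename or split the flag.

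**The concern.** The definition still calls the excluded events SADEs, so the plan has two event sets: all adjudicated SADEs, and those that count for the rate. One yes/no variable with one label serves both, and neither its label nor that of the first-event date mentions relevance. Read literally, the label would let excluded events into the rate. Read as restricted, the row in the later table would miss patients although it says any.

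The rate is the plan's main safety summary, and SAP chapter 5 (12.16) also compares it between higher- and lower-enrolling groups. If its event set were open, a reader could not tell what the rate and interval describe. The Erratum's condition for the extra binomial interval could be doubtful in the same way.

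**Working it through.** The documents give no SADE count and no SADE-free rate, so there is no planned figure to reproduce. The check is mainly on the text, with an illustration of size.

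**Step 1: where the two uses can differ.**

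| Patient's adjudicated SADEs | Value needed for the rate | Value needed for an unrestricted any-SADE row |
|---|---|---|
| None | No | No |
| At least one relevant | Yes | Yes |
| Only not relevant | No | Yes |

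Only the third kind of patient matters. That group may be small. The adjudication re-examines device relatedness, and the only relatedness field shown from its file is relation to the investigational device (`aerelidv`). A purely procedural event judged unrelated to the device may therefore not count as an adjudicated SADE at all. The group is then mainly patients with device-related events excluded for an external influence, another causative event or Twiddler's syndrome.

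**Step 2: which set the plan leads to for the rate.** The heading of 11.2 points to the definition, and the definition comes first. The derivation inputs listed directly after it are the onset date and `aerelset`. Seriousness (`aeser`) and device relation (`aerelidv`) are not in that table; they appear only in the listing table. An unrestricted flag or first-event date cannot be built from the listed inputs, whereas a restricted one follows at once: `any_sade_SAR` = Yes if any record has `aerelset` = Yes, and `date_1stsade_SAR` = the earliest onset date among those records.

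**Step 3: size if the definition were ignored.** Inputs: N = 50 (planned enrolment, CIP 8.2.3 as quoted in CIP Amendment 2) and binomial intervals (SAP chapter 5, 12.3). Assumed: everyone is followed for 12 months and there is no relevant SADE. For x event-free patients of n, the exact 95% limits are the 0.025 quantile of Beta(x, n − x + 1) and the 0.975 quantile of Beta(x + 1, n − x). For x = n the lower limit is 0.025^(1/n).

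- Restricted, as defined: 50/50 = 100%, lower limit 0.025^(1/50) = 92.89%.
- Unrestricted, one such patient: 49/50 = 98.0% (89.35 to 99.95).
- Unrestricted, two: 48/50 = 96.0% (86.29 to 99.51).
- In an enrolment half of about 25: 25/25 = 100% (lower limit 0.025^(1/25) = 86.28%) against 24/25 = 96.0% (79.65 to 99.90).

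Every figure below 100% requires events that the definition excludes.

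**Step 4: the date.** Take 50 patients, one with a not-relevant SADE on day 100, one with a relevant SADE on day 200, and the rest followed past day 365. Kaplan-Meier at 12 months:

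- Restricted flag and date: 1 − 1/50 = 98.0%.
- Unrestricted flag and date: (49/50) × (48/49) = 96.0%.
- Restricted flag with an unrestricted date: 1 − 1/49 = 97.96%.

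The mixed case differs from the correct value by 0.04 points, and Step 2 rules it out because flag and date come from the same records.

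**Step 5: the Erratum's condition.** It stands under the 11.2 heading, whose definition governs which SADEs are meant. SAP 11.2 already attaches a 95% interval to `any_sade_SAR`, and 12.3 makes that interval binomial. A not-relevant SADE would therefore not remove the interval for the full analysis set. At most it could affect the added calculation in patients with a documented 12-month visit.

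**The case for a change.** The best argument for a change rests on the labels. The later table uses the same reference to internal adjudication for `any_ade_SAR`, which includes non-serious effects. A non-serious effect cannot be relevant to a SADE-free rate, so the phrase cannot stand for the relevance restriction there, and `any_sade_SAR` beside it reads naturally as all adjudicated SADEs. SAP 2.4 asks for a construction rule for each derived variable, and none is visible here. No single rule could serve an unrestricted row and a restricted rate together, and the Erratum drops the dated listing of excluded events.

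Part of this stands: the label fits the later table better than the rate, and if the flag is restricted in both places that row can omit a patient.

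The rest carries less weight. A missing rule cannot be held against the plan on this text, because boxes have plainly dropped out of it: 11.20 and its Erratum version both point to content below that is not there. A lost box could have set the same restriction for both tables, leaving only the label. Excluded events also stay visible. The Erratum reports `aeser`, `aerelidv` and `aerelset` with the reasons for a negative decision, and 11.13 assigns adverse events to a separate safety report from the Vigilance Department. If `n_sade_SAR` counts all SADEs, a patient with a count of one or more and a flag of No would show the mismatch in the same table. Restoring the dated listing is a preference.

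**Conclusion.** No change to the plan is needed. The SADE-free rate, its interval and the 12.16 comparison are fixed by the definition that opens 11.2 and by the relevance input listed for them, so the effect on the rate is zero when it is derived as defined. What is left is a labelling point on one descriptive row. With 50 patients, a restricted flag would understate that row by 1/50 = 2 percentage points for each patient whose only SADEs are not relevant, and by nothing if there is no such patient.

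This rests on two assumptions: that analysts apply the quoted definition, and that the table of derivation inputs means what SAP 2.4 says such tables mean. The documents do not show whether any patient of the critical kind exists. The study has no endpoints, hypotheses or pass/fail criteria, and all analyses are exploratory, so no decision rule depends on the row. A statistician programming the tables would see which event set each row needs and can state it in the table title or footnote.
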